#### **Definition of SAE**

If an event is not an AE per definition above, then it cannot be an SAE even if serious conditions are met (e.g., hospitalization for signs/symptoms of the disease under study, death due to progression of disease).

An SAE is defined as any untoward medical occurrence that, at any dose:

- Results in Death
  - O The term 'life-threatening' in the definition of 'serious' refers to an event in which the subject was at risk of death at the time of the event. It does not refer to an event, which hypothetically might have caused death, if it were more severe.
- Requires in subject hospitalization or prolongation of existing hospitalization
  - o In general, hospitalization signifies that the subject has been detained (usually involving at least an overnight stay) at the hospital or emergency ward for observation and/or treatment that would not have been appropriate in the physician's office or ambulatory care setting. Complications that occur during hospitalization are AEs. If a complication prolongs hospitalization or fulfills any other serious criteria, the event is serious. When in doubt as to whether "hospitalization" occurred or was necessary, the AE should be considered serious. Hospitalization for elective treatment of a pre-existing condition that did not worsen from baseline is not considered an AE.
- Results in persistent disability/incapacity
  - The term disability means a substantial disruption of a person's ability to conduct normal life functions.
  - This definition is not intended to include experiences of relatively minor medical significance such as uncomplicated headache, nausea, vomiting, diarrhea, influenza, and accidental trauma (e.g., sprained ankle) which may interfere with or prevent everyday life functions but do not constitute a substantial disruption.
- Is a congenital anomaly/birth defect
- Other situations:
  - Medical or scientific judgment should be exercised in deciding whether SAE reporting is appropriate in other situations such as important medical events that may not be immediately life-threatening or result in death or hospitalization but may jeopardize the subject or may require medical or surgical intervention to prevent one of the other outcomes listed in the above definition. These events should usually be considered serious. Examples of such events include invasive or malignant cancers, intensive treatment in an emergency room or at home for allergic bronchospasm, blood dyscrasias or convulsions that do not result in hospitalization, or development of drug dependency or drug abuse.

## Recording an AE and/or SAE

- When an AE/SAE occurs, it is the responsibility of the investigator to review all documentation (e.g., hospital progress notes, laboratory reports, and diagnostics reports) related to the event.
- The investigator will then record all relevant AE/SAE information in the CRF.
- It is not acceptable for the investigator to send photocopies of the subject's medical records to the safety team in lieu of completion of the safety team/AE/SAE CRF page.
- There may be instances when copies of medical records for certain cases are requested by the safety team. In this case, all subject identifiers, with the exception of the subject number, will be redacted on the copies of the medical records before submission to the safety team.
- The investigator will attempt to establish a diagnosis of the event based on signs, symptoms, and/or other clinical information. Whenever possible, the diagnosis (not the individual signs/symptoms) will be documented as the AE/SAE.

# **Assessment of Intensity**

The investigator will make an assessment of intensity for each AE and SAE reported during the study and assign it to one of the following categories:

- Mild: An event that is easily tolerated by the subject, causing minimal discomfort and not interfering with everyday activities.
- Moderate: An event that causes sufficient discomfort and interferes with normal everyday activities.
- Severe: An event that prevents normal everyday activities. An AE that is assessed as severe should not be confused with a SAE. Severe is a category utilized for rating the intensity of an event; and both AEs and SAEs can be assessed as severe.
- An event is defined as 'serious' when it meets at least one of the predefined outcomes as described in the definition of an SAE, NOT when it is rated as severe.

# **Assessment of Causality**

- The investigator is obligated to assess the relationship between study treatment and each occurrence of each AE/SAE.
- The investigator will use clinical judgment to determine the relationship.
  - O Unlikely A clinical event, including laboratory test abnormality, with a temporal relationship to drug administration which makes a causal relationship improbable, and in which other drugs, chemicals or underlying disease provide plausible explanations. For the purpose of this protocol, the term unlikely will be considered not related to study medication and an "Adverse Event"
  - O Possible A clinical event, including laboratory test abnormality, with a reasonable time sequence to administrations of the drug, but which could also be explained by concurrent disease or other drugs or chemicals. Information on drug withdrawal may be lacking or unclear. For the purpose of this protocol an event that has possible relationship to study medication will be defined as a "Suspected Adverse Drug Reaction".
  - O Probable A clinical event, including laboratory test abnormality, with a reasonable time sequence to administration of the drug, unlikely to be attributed to concurrent disease or other drugs or chemicals, and which follows a clinically reasonable response on withdrawal. For the purpose of this protocol an event that has probable relationship to study medication will be defined as an "Adverse Drug Reaction".

- Definite This category applies to those AEs which are considered "definitely related" to
  the test drug. The relationship of an AE to study drug may be considered definite, if it
  meets the criteria for "probable" with a definite certainty as to the relationship to the test
  drug.
- Unrelated This category is applicable to those AEs that are judged to be clearly and incontrovertibly due only to extraneous causes (disease, environment, etc.) and do not meet the criteria for drug relationship listed under Unlikely, Possible, Probable, or Definite.
- Alternative causes, such as underlying disease(s), concomitant therapy, and other risk factors, as well as the temporal relationship of the event to study treatment administration will be considered and investigated.
- The investigator will also consult the Investigator's Brochure (IB) and/or Product Information, for marketed products, in his/her assessment.
- For each AE/SAE, the investigator must document in the medical notes that he/she has reviewed the AE/SAE and has provided an assessment of causality.
- There may be situations in which an SAE has occurred, and the investigator has minimal information to include in the initial report to the safety team. However, it is very important that the investigator make an assessment of causality for every event before the initial transmission of the SAE data to the safety team.
- The investigator may change his/her opinion of causality in light of follow-up information and send a SAE follow-up report with the updated causality assessment.
- The causality assessment is one of the criteria used when determining regulatory reporting requirements.

## Follow-up of AEs and SAEs

- The investigator is obligated to perform or arrange for the conduct of supplemental measurements and/or evaluations as medically indicated or as requested by safety team to elucidate the nature and/or causality of the AE or SAE as fully as possible. This may include additional laboratory tests or investigations, histopathological examinations, or consultation with other health care professionals.
- If a subject dies during participation in the study or during a recognized follow-up period, the investigator will provide the safety team with a copy of any post-mortem findings including histopathology.
- New or updated information will be recorded in the originally completed CRF.
- The investigator will submit any updated SAE data to the sponsor within 24 hours of receipt of the information.

## SAE Reporting to the Safety Team via an Electronic Data Collection Tool

- The primary mechanism for reporting an SAE to the safety team will be the electronic data collection tool
- If the electronic system is unavailable for more than 24 hours, then the site will use the paper SAE data collection tool (see next section).
- The site will enter the SAE data into the electronic system as soon as it becomes available.

- After the study is completed at a given site, the electronic data collection tool will be taken offline to prevent the entry of new data or changes to existing data.
- If a site receives a report of a new SAE from a study subject or receives updated data on a previously reported SAE after the electronic data collection tool has been taken off-line, then the site can report this information on a paper SAE form located within the Investigator Site File.
- Contacts for SAE reporting can be found in the project team list within the Investigator Site File.

# **SAE Reporting to the Safety Team via Paper CRF**

- Facsimile transmission of the SAE paper CRF is the preferred method to transmit this information to the safety monitor.
- In rare circumstances and in the absence of facsimile equipment, notification by telephone is acceptable with a copy of the SAE data collection tool sent by overnight mail or courier service.
- Initial notification via telephone does not replace the need for the investigator to complete and sign the SAE CRF pages within the designated reporting time frames.
- Contacts for SAE reporting can be found in the study reference manual.

# **APPENDIX 3: STUDY GOVERNANCE CONSIDERATIONS**

# **Regulatory and Ethical Considerations**

- This study will be conducted in accordance with the protocol and with the following:
  - Consensus ethical principles derived from international guidelines including the Declaration of Helsinki and Council for International Organizations of Medical Sciences (CIOMS) International Ethical Guidelines
  - o Applicable ICH Good Clinical Practice (GCP) Guidelines
- The protocol, protocol amendments, ICF, Investigator Brochure, and other relevant documents (e.g., advertisements) must be submitted to an IRB/IEC by the investigator or CRO and reviewed and approved by the IRB/IEC before the study is initiated.
- Any amendments to the protocol will require IRB/IEC approval before implementation of changes made to the study design, except for changes necessary to eliminate an immediate hazard to study subjects.
- The investigator will be responsible for the following:
  - Providing written summaries of the status of the study to the IRB/IEC annually or more frequently in accordance with the requirements, policies, and procedures established by the IRB/IEC
  - Notifying the IRB/IEC of SAEs or other significant safety findings as required by IRB/IEC procedures
  - Providing oversight of the conduct of the study at the site and adherence to requirements of 21 CFR, ICH guidelines, the IRB/IEC, European regulation 536/2014 for clinical studies (if applicable), and all other applicable local regulations

## **Financial Disclosure**

Investigators and sub-investigators will provide the sponsor with sufficient, accurate financial information as requested to allow the sponsor to submit complete and accurate financial certification or disclosure statements to the appropriate regulatory authorities. Investigators are responsible for providing information on financial interests during the course of the study and for one year after completion of the study.

## **Informed Consent Process**

- The investigator or his/her representative will explain the nature of the study to the subject or his/her legally authorized representative and answer all questions regarding the study.
- Subjects must be informed that their participation is voluntary. Subjects or their legally authorized representative will be required to sign a statement of informed consent that meets the requirements of 21 CFR 50, local regulations, ICH guidelines, Health Insurance Portability and Accountability Act (HIPAA) requirements, where applicable, and the IRB/IEC or study center.

- The medical record must include a statement that written informed consent was obtained before the subject was enrolled in the study and the date the written consent was obtained. The authorized person obtaining the informed consent must also sign the ICF.
- Subjects must be re-consented to the most current version of the ICF(s) during their participation in the study.
- A copy of the ICF(s) must be provided to the subject or the subject's legally authorized representative.
- Any remaining study samples cannot be used for optional exploratory research.
- Subjects who are rescreened are required to sign a new ICF and will be given a new screening number.

#### **Data Protection**

- Subjects will be assigned a unique identifier by the sponsor. Any subject records or datasets that are transferred to the sponsor will contain the identifier only; subject names or any information which would make the subject identifiable will not be transferred.
- The subject must be informed that his/her personal study-related data will be used by the sponsor in accordance with local data protection law. The level of disclosure must also be explained to the subject.
- The subject must be informed that his/her medical records may be examined by Clinical Quality Assurance auditors or other authorized personnel appointed by the sponsor, by appropriate IRB/IEC members, and by inspectors from regulatory authorities.

# **Data Quality Assurance**

- All subject data relating to the study will be recorded on electronic CRF unless transmitted to the sponsor or designee electronically (e.g., laboratory data). The investigator is responsible for verifying that data entries are accurate and correct by physically or electronically signing the CRF and dating it.
- The investigator must maintain accurate documentation (source data) that supports the information entered in the CRF.
- The investigator must permit study-related monitoring, audits, IRB/IEC review, and regulatory agency inspections and provide direct access to source data documents.
- The sponsor or designee is responsible for the data management of this study including quality checking of the data.
- Study monitors will perform ongoing source data verification to confirm that data entered into the CRF by authorized site personnel are accurate, complete, and verifiable from source documents; that the safety and rights of subjects are being protected; and that the study is being conducted in accordance with the currently approved protocol and any other study agreements, ICH GCP, and all applicable regulatory requirements.
- Records and documents, including signed ICFs, pertaining to the conduct of this study must be retained by the investigator in accordance with all state, federal and local laws and FDA guidance

after study completion unless local regulations or institutional policies require a longer retention period. No records may be destroyed during the retention period without the written approval of the sponsor. No records may be transferred to another location or party without written notification to the sponsor.

## **Source Documentation**

- Source documents provide evidence for the existence of the subject and substantiate the integrity of the data collected. Source documents are filed at the investigator's site.
- Data reported on the CRF or entered in the eCRF that are transcribed from source documents must be consistent with the source documents or the discrepancies must be explained. The investigator may need to request previous medical records or transfer records, depending on the study. Also, current medical records must be available.
- A source document can be almost anything. It is the original place or "source" where information is recorded.

# **Study and Site Closure**

The Sponsor designee reserves the right to close the study site or terminate the study at any time for any reason at the sole discretion of the sponsor. Study sites will be closed upon study completion. A study site is considered closed when all required documents and study supplies have been collected and a study-site closure visit has been performed.

The investigator may initiate study-site closure at any time, provided there is reasonable cause and sufficient notice is given in advance of the intended termination.

Reasons for the early closure of a study site by the sponsor or investigator may include but are not limited to:

- Failure of the investigator to comply with the protocol, the requirements of the IRB/IEC or local health authorities, the sponsor's procedures, or GCP guidelines
- Inadequate recruitment of subjects by the investigator
- Discontinuation of further study treatment development

## APPENDIX 4: STANDARD OF CARE

Standard of care (SOC) Treatment consists of:

- Moist wound dressings,
- debridement of necrotic/non-viable tissue
- infection surveillance and management and
- offloading of weight bearing from vicinity of the ulcer.

The site will document that a weekly Test Product kit was used and that they provided materials and training to the subject and care giver, as applicable. Beginning at the screening visit, all subjects must have their study ulcer managed using the SOC procedures noted below.

# **Cleaning the Study Ulcer**

Microbiology and microflora swabs will be obtained before cleansing the wound and/or debridement. The leg should be elevated for as much time as possible during this process. The ulcer and peri ulcer area will be cleansed to minimize bioburden and maceration. The investigator or designee will irrigate the ulcer with sterile normal saline solution. Sterile gauze will be used to pat the ulcer dry.

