For all visits during the treatment period, if subjects are seen at the clinic before mid-day, they will not replace the dressing applied the evening before prior to the clinic visit, until after the visit procedures are complete. The site staff or caregiver will then apply the morning dressing.

If subjects are seen at the clinic after mid-day, they will replace the gel dressing in the morning. After all the visit procedures are complete the site staff or caregiver will apply the evening dressing and this will be left in place until the following morning.

Test Product will not be applied on the morning of the final EOT visit or the ET visit. Sharp Excisional Debridement is required at V1, permitted at V2 and prohibited thereafter. Light Debridement is permitted at V3 – V6

No debridement is allowed at V7 or ET

Sharp excisional debridement or light sharp scalpel debridement is permitted at V8

Adherence to the study design requirements, including those specified in Schedule of Events, is essential and required for study conduct.

Immediate safety concerns should be discussed with the sponsor immediately upon occurrence or awareness to determine if the subject should continue or discontinue study treatment.

All screening evaluations must be completed and reviewed to confirm that potential subjects meet all eligibility criteria. The investigator will maintain a screening log to record details of all subjects screened and to confirm eligibility or record reasons for screening failure, as applicable.

Procedures conducted as part of the subject's routine clinical management (e.g., blood count) and obtained before signing of the ICF may NOT be utilized for screening or baseline purposes. Study procedures and their timing are summarized in Schedule of Events. Protocol waivers or exemptions are not allowed.

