#### General Information Visits 3-7:

Eligible subject's caregivers will apply Test Product twice daily, approximately 12 hours apart and at approximately the same times each day. Test Product will be applied topically to the target ulcer from a single dose applicator. The target ulcer will be dressed with Mepitel or equivalent which will be trimmed to cover the entire dimension of the ulcer and overlaid into the ulcer, followed by Tegaderm dressing covering the entire dimension of the ulcer. Padding and Coban Lite 2- layer dressing or equivalent will be placed over the Mepitel, or equivalent, covered with Tegaderm.

The subject and caregiver will be instructed to leave the bandage on the wound until applying the next dose and thereafter morning and evening for 28 days. Subjects and caregivers will be given written instructions on the proper care and hygiene to include keeping the ulcer clean and bandage dry at V3. The subject WILL NOT apply gel or change dressing on the day of their final visit.

Standardized offloading will continue over the course of the study. For all visits during the treatment period, if subjects are seen at the clinic before mid-day, the caregiver will not replace the dressing applied the evening before prior to the clinic visit, until after the visit procedures are complete. The caregiver will then apply the morning dressing.

If subjects are seen at the clinic after mid-day, they will replace the gel dressing in the morning. After all the visit procedures are complete the caregiver will apply in the clinic the evening dressing and leave in place until the following morning.

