#### Visit 1 (Day -14 prior to baseline (+/- 2 days)) Screening:

- Informed consent and confirmation of eligibility
- Baseline subject disease assessments (as specified in the Schedule of Events table)
- Collect Demographic Data
- Twelve-month medical history
- Targeted physical examination: Perform a physical exam.
- Vital signs measurements: Weight, temperature, resting blood pressure, heart rate, and respiratory rate. Vital signs are to be obtained prior to collecting laboratory samples.
- Safety Laboratory Tests including tests noted in section 11.5.4
- For females of child-bearing potential: the pregnancy test (serum) performed at screening
- Selection of the target ulcer
- Screening Ulcer Assessment: Visual examination of selected target ulcer before and after debridement.
- The target ulcer is classified according to the Wagner Scale.

- Two wound swabs, one for culture and one for microflora examination will be taken BEFORE debridement or any cleansing. Samples collected in accordance with the Microbiological Assessment Appendix 5
- Sharp excisional debridement in accordance with debridement section of the Standard of Care Appendix 4
- Digital photos taken before and after debridement by site staff. Two photos are to be taken from a focal distance of 18 inches, and one photo taken close-up for a total of three digital images
- Employ an advanced digital imaging system to accurately measure the target foot ulcer dimensions following debridement
- Measure Transcutaneous oxygen pressures (TcPO2), obtain Ankle brachial pressure index or biphasic/triphasic doppler ultrasound
- Subject and care giver trained in application of dressing in accordance with the Appendix 4
- Hydrogel and SOC dressing applied in accordance with the Standard of Care Appendix 4
- Review and dispense subject instruction sheet
- Record all adverse events (local and systemic), concurrent procedures, and changes in concomitant medications on the source documents and case report forms (eCRFs)
- Dispense offloading RCW accordance with Appendix 6 and review expectations
- Begin offloading in accordance with Appendix 6

Visit 2 (Day -7 (+/- 2 days)) Run-In: All subjects will return to the clinic to be seen for wound care and ulcer examination. The following assessments will be completed at this visit.

- Vital signs measurements: Weight, temperature, resting blood pressure, heart rate, and respiratory rate

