- The caregiver will be observed applying the first dose in the clinic to ensure compliance administering Test Product topically to the diabetic foot ulcer and surrounding intact skin. The target ulcer will be dressed with Mepitel, or equivalent, which will be trimmed to cover the entire dimension of the ulcer and overlaid into the ulcer, followed by Tegaderm dressing covering the entire dimension of the ulcer. Padding and Coban Lite 2- layer dressing or equivalent will be placed over the Mepitel, or equivalent, covered with Tegaderm
- The subject will be scheduled for the next study visit, with a reminder to bring the test article kit, including all tubes, whether they are empty, partially empty and/or unused tubes to the visit
- Record all adverse events (local and systemic), concurrent procedures, and changes in concomitant medications during the study on the source documents and case report forms (eCRFs)
- Continue offloading applied in accordance with Appendix 6

Visit 4 (Day 7±2 days.): Subjects will return after applying test product for 7 (+/- 2) days every 12 hours. Subject disease assessments will be performed as specified in the schedule of events table.

- Vital signs measurements: Weight, temperature, resting blood pressure, heart rate, and respiratory
- Ulcer Assessment: Visual examination of chronic ulcer before and after light debridement (if necessary)
- Light debridement, only if required
- Digital images should be taken pre and post debridement with the sponsor provided digital camera, if debridement is required. Two photos are to be taken from a focal distance of 18 inches, and one photo taken close-up for a total of three digital images
- Employ an advanced digital imaging system to accurately measure the target foot ulcer dimensions following debridement (if debridement is required)
- Collect Test Product kit dispensed on Day 0, determine accountability
- Subjects will be provided with his/her second designated test product kit and instructed to apply the product twice daily for 1 week (7±2 days)

- Two wound swabs, one for culture and one for microflora examination are taken BEFORE debridement, if the wound is still open
- The subject will be scheduled for the next study visit, with a reminder to bring the test article kit and tubes, including empty, partially used, and unused tubes to the visit

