# **APPENDIX 5: MICROBIOLOGICAL ASSESSMENTS**

Two wound swabs of ulcer will be sent for aerobic and anaerobic cultures of contaminating microbes, which will be performed by a central microbiology lab, and for molecular evaluation of microflora at V1, V3, V4, V5, V6 and V7 (and/or at early termination). Suitable culture samples must be obtained via wound swab. Biopsy, curettage, and needle aspirations are not allowed. If suitable culture material is not available due to healing of the ulcer, this will be documented by the investigator. All wound swabs will be obtained BEFORE debridement.

The eradication/persistence of each baseline pathogenic species will be determined based on culture results reported by the laboratory. If a subject's culture result is missing for V7, the baseline pathogen will be presumed eradicated if a) ulcer closure is achieved, b) because of ulcer healing there is a lack of suitable tissue sample/culturable material (as documented by the investigator), or c) the culture result is otherwise missing, and pathogen eradication was achieved in the last available culture result. In all other circumstances, baseline pathogen persistence (i.e., not eradication) will be presumed.

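### On-treatment culture swabs are taken before any rinse from ulcers still under the last gel dose; neither document controls Nu-3 carry-over, which would favour the active arms if it occurs

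*Protocol*

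**What the plan says.** **Order of sampling.** Protocol Appendix 4 (Cleaning the Study Ulcer) sets the general order: "Microbiology and microflora swabs will be obtained before cleansing the wound and/or debridement". Saline irrigation is described after that. Appendix 5 adds: "All wound swabs will be obtained BEFORE debridement". The lists for Visits 4, 5 and 6 in Section 8 read: "Two wound swabs, one for culture and one for microflora examination are taken BEFORE debridement, if the wound is still open". The more explicit phrase "will be taken BEFORE debridement or any cleansing" belongs to Visit 1 only.

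**What is on the ulcer.** During treatment, subject and caregiver are told to "leave the bandage on the wound until applying the next dose" (Section 8, General Information Visits 3-7). Section 5.4 says of visits before mid-day that "they will not replace the dressing applied the evening before prior to the clinic visit, until after the visit procedures are complete". For later visits: "If subjects are seen at the clinic after mid-day, they will replace the gel dressing in the morning". No gel may be applied on the day of Visit 7 or of an early termination visit (Synopsis, Administration). Section 8 also bars a dressing change on the day of the final visit.

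**Use of the cultures.** Appendix 5: "The eradication/persistence of each baseline pathogenic species will be determined based on culture results reported by the laboratory". If the Visit 7 culture is missing without healing as the reason, eradication in the last available culture counts as eradication. The SAP has no eradication analysis. It summarises and models colony counts (weeks 1 to 4, with week 0 as a factor) and lists species and susceptibilities.

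**What is left open.** The protocol refers obtaining, storing and shipping of swabs to the study reference manual. Neither document mentions a neutralising medium, a pre-culture rinse or a carry-over check.

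**The concern.** A culture swab from an unrinsed ulcer picks up gel as well as organisms. In the active arms that gel contains an agent which Section 3.1 describes as directly bactericidal. If enough drug travels with the swab and stays active, organisms alive in the ulcer may fail to grow in the laboratory, and the result looks the same as killing in the wound.

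The two usual safeguards do not help. Placebo gel is matched on pH, so acidity effects cancel, but it contains no Nu-3. The screening and baseline swabs precede any Nu-3, so adjusting for week 0 removes nothing. The nominal strength also doubles from cohort 1 to cohort 2, so carry-over, if it rises with strength, could resemble a dose response.

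At stake is the antimicrobial secondary objective. The SAP (Research hypotheses) says two secondary endpoints will be tested, one of them conditionally. The conditional one is the logrank test on time to heal; by elimination, the unconditional one appears to be the bacterial count model.

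**Working it through.** The documents give no figure to reproduce here. The check is a comparison of the rules by visit, followed by an illustration of what a given amount of carry-over would do.

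**1. Exposure at each swab**

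| Swab | Last gel on the ulcer | Nu-3 possible on an active-arm swab | On a placebo swab |
|---|---|---|---|
| Visit 1 | No study gel yet | No | No |
| Visit 3 (baseline) | Commercial hydrogel | No | No |
| Visits 4-6, before mid-day | Previous evening's dose, about 12 h | Yes | No |
| Visits 4-6, after mid-day | Same morning's dose | Yes | No |
| Visit 7 | Previous evening's dose, about 12 h or more | Yes | No |
| Early termination | Previous day's dose or older | Yes, if recently dosed | No |

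The contrast between active and placebo arms holds at every on-treatment visit. It is strongest at afternoon Visits 4 to 6, which supply up to three of the four post-baseline count time points.

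**2. How much drug could be carried (assumed)**

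The 5% gel holds 50 mg/g and the 10% gel 100 mg/g, so a 4 g applicator holds 200 mg or 400 mg. Assume that 0.01 to 0.1 g of gel enters 1 mL of medium:
- 5%: 0.5 to 5 mg in 1 mL = 500 to 5,000 µg/mL
- 10%: 1 to 10 mg in 1 mL = 1,000 to 10,000 µg/mL
- with 99% of the drug already lost: 5 to 50 and 10 to 100 µg/mL

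The residue, volume and loss are assumptions. The documents give no inhibitory concentration, so these figures cannot be turned into a share of suppressed cultures.

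**3. Effect on eradication (assumed e and f)**

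Let e be the true eradication proportion, equal in all arms, and f the share of truly persistent active-arm cultures that carry-over suppresses. Then apparent active eradication = e + (1 − e)f, and the false difference = (1 − e)f. With e = 0.20 and 24 active subjects (2 × 12):

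| f | Apparent active | Placebo | False difference | False eradications, 24(1 − e)f |
|---|---|---|---|---|
| 0 | 20% | 20% | 0 | 0 |
| 0.10 | 28% | 20% | 8 points | 1.9 |
| 0.20 | 36% | 20% | 16 points | 3.8 |
| 0.30 | 44% | 20% | 24 points | 5.8 |
| 0.50 | 60% | 20% | 40 points | 9.6 |

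Over e = 0.10 to 0.30 and f = 0.10 to 0.50 the false difference runs from 0.70 × 0.10 = 7 points to 0.90 × 0.50 = 45 points.

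**4. Effect on counts (assumed shift and SD)**

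Take a simple two-sided t comparison at 0.05, 24 active against 8 placebo, df = 30. The noncentrality is shift / (SD × √(1/24 + 1/8)) = shift / (0.408 × SD). With no true effect, the probability of p < 0.05 is:

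| Carry-over shift (log10 CFU) | SD 1.0 | SD 1.5 | SD 2.0 |
|---|---|---|---|
| 0 | 5% | 5% | 5% |
| 0.5 | 22% | 12% | 9% |
| 1.0 | 66% | 35% | 22% |
| 2.0 | 99.7% | 89% | 66% |

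This stands in for the SAP's repeated-measures model, whose terms are not specified closely enough to simulate. It shows sensitivity to a given shift, not that a shift exists.

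**The case against.** The case against has several parts.

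- **The manual may already deal with it.** This stands. Swabbing before cleansing rules out a rinse at that step but not a neutralising transport medium, which is the kind of detail a manual or central laboratory would set. The documents therefore show a missing control, not a missing practice.
- **The effect could be zero.** This stands. On the assumed figures the carried concentration is 10 to 100 times below nominal gel strength (50,000 µg/mL at 5%, against 500 to 5,000), and the organisms have already survived the dressing period. That lowers the plausibility without settling it: the concentration actually reaching them in the ulcer is not given, and surviving exposure is not the same as growing in the presence of drug.
- **Visit 7, which decides eradication, bars same-day gel.** True, and exposure is lower there. But the dressing from the evening before is still in place, and Visits 4 to 6 feed the count model and the last-available-culture rule.
- **A second swab goes for molecular evaluation, which needs no growth.** True, so the antimicrobial objective does not rest on culture alone. But neither the eradication rule nor the count model uses it.
- **Rinsing changes what is measured.** True. Irrigation is meant to reduce the microbial load, so counts would fall and more samples could drop below detection, possibly unequally if true counts differ by arm.

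A reader might go further and infer that the cultures will show false eradication, that the direction of error is certain, or that dose escalation is compromised. The documents do not support this. They support only that carry-over, if it occurs, favours Nu-3. Escalation rests on safety data and dose-limiting toxicity criteria; only the final dose recommendation draws on all data.

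**Conclusion.** The point holds as an uncontrolled risk to a secondary endpoint. The stated order of procedures allows Nu-3 to reach the culture in the active arms at Visits 4 to 7 and never on placebo or at baseline. If growth is suppressed, the error favours Nu-3 in the colony counts, in the species listings so far as they come from culture, and in the Appendix 5 eradication rule.

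The size cannot be fixed from the documents. The illustrative ranges (7 to 45 points for eradication; 9% to 99.7% false significance for count shifts of 0.5 to 2.0 log10) depend wholly on assumed values of e, f, shift and SD. Primary safety is unaffected. This is a cheap improvement to make, not a defect that invalidates the trial.

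**What to change.** Choose one of two routes and write it into Appendix 4 (Cleaning the Study Ulcer) and Appendix 5.

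1. **Rinse first.** Keep the molecular microflora swab before cleansing. Take the culture swab after the saline irrigation already described and before debridement, identically in all arms and at every swab visit, including Visits 1 and 3. The Visit 1 wording in Section 8 would need to match.
2. **Neutralise.** Keep the present order and require a culture transport medium that the central laboratory confirms neutralises Nu-3. If the manual already specifies one, cite it in Appendix 5.

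Under either route, record the time since last dose at each swab, and add to the SAP a sensitivity comparison of culture with the molecular result. That comparison supports interpretation but cannot by itself separate carry-over from true killing, since both can leave a molecular signal without growth. Looking at it by time since last dose would help.

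**Cost.** A short amendment, one data field and a few lines in the SAP; no extra visit and no change to treatment. Route 1 lowers recovered surface counts and may put more samples below detection. Route 2 avoids that but needs laboratory confirmation. The choice should be in force before swabs are collected: organisms that failed to grow cannot be recovered in analysis, and because cohorts run in sequence, a change between them would confound sampling method with dose.
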